10.1.1 Adverse events

An AE is any untoward medical occurrence (e.g., any unfavorable and unintended sign [including abnormal laboratory findings], symptom or disease) in a patient or clinical investigation patient after providing written informed consent for participation in the study. Therefore, an AE may or may not be temporally or causally associated with the use of a medicinal (investigational) product.

The investigator has the responsibility for managing the safety of individual patient and identifying AEs.

Novartis qualified medical personnel will be readily available to advise on trial related medical questions or problems.

The occurrence of AEs must be sought by non-directive questioning of the patient at each visit during the study. Adverse events also may be detected when they are volunteered by the patient during or between visits or through physical examination findings, laboratory test findings, or other assessments.

Adverse events must be recorded under the signs, symptoms or diagnosis associated with them, accompanied by the following information (as far as possible) (if the event is serious refer to [Section 10.1.2](#)):

1. Adverse events will be assessed and graded according to the CTCAE version 4.03
2. its relationship to the study treatment
3. its duration (start and end dates) or if the event is ongoing, an outcome of not recovered/not resolved must be reported.
4. whether it constitutes a SAE (see [Section 10.1.2](#) for definition of SAE) and which seriousness criteria have been met
5. action taken regarding study treatment.

All adverse events must be treated appropriately. Treatment may include one or more of the following:

- Dose not changed
- Dose reduced/increased
- Drug interrupted/withdrawn

6. its outcome i.e., its recovery status or whether it was fatal

Conditions that were already present at the time of informed consent should be recorded in medical history of the patient.

Adverse events (including lab abnormalities that constitute AEs) should be described using a diagnosis whenever possible, rather than individual underlying signs and symptoms.

Adverse event monitoring should be continued for at least 30 days following the last dose of study treatment.

Once an adverse event is detected, it must be followed until its resolution or until it is judged to be permanent (e.g. Continuing at the end of the study), and assessment must be made at each

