visit (or more frequently, if necessary) of any changes in severity, the suspected relationship to the interventions required to treat it, and the outcome.

Information about adverse drug reactions for the investigational drug can be found in the IB.

Abnormal laboratory values or test results constitute adverse events only if they fulfill at least one of the following criteria:

- they induce clinical signs or symptoms
- they are considered clinically significant
- they require therapy

Clinically significant abnormal laboratory values or test results must be identified through a review of values outside of normal ranges, significant changes from baseline or the previous visit, or values which are considered to be non-typical in patients with the underlying disease.

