12.5.2 Safety endpoint(s)

Safety summary tables include only data from the on-treatment period with the exception of baseline data which will also be summarized where appropriate.

The on-treatment period lasts from the date of first dose of eltrombopag to 30 days after the date of the last dose of eltrombopag.

Adverse events

All information obtained on adverse events will be displayed by patient. Summary tables for adverse events (AEs) will include only AEs that started or worsened during the on-treatment period, the **treatment-emergent** AEs (TEAEs).

The incidence of TEAEs will be summarized by system organ class (SOC) and or preferred term, severity based on the CTCAE grades, type of adverse event and relation to eltrombopag.

Serious adverse events, AEs leading to discontinuation, AEs leading to dose adjustment and adverse events of special interest (AESI) which includes bleeding events during the on-treatment period will be tabulated.

Specific groupings of AESI will be considered and the number of patients with at least one event in each grouping will be reported. Such groups consists of AEs for which there is a specific clinical interest in connection with eltrombopag treatment or AEs which are similar in nature (although not identical). Note that certain AEs may be reported within multiple groupings/AESIs.

AESIs are defined by MedDRA terms. Definition for retrieval and maintenance is done in the electronic case retrieval sheet (eCRS).

The incidence of AESIs will be summarized by SOC and Preferred Term (PT).

The AESIs as specified in the latest version of the case retrieval sheet (CRS) at the time of analysis will be used.

All deaths (on-treatment and post-treatment [starting at day 30+1 after last dose of eltrombopag]) will be summarized.

All AEs, deaths and SAEs will be listed and those collected during the pre-treatment (from day of patient's informed consent to the day before first dose of eltrombopag) and post-treatment period will be flagged.

A patient with multiple AEs within a primary SOC is only counted once towards the total of the primary SOC.

Clinical laboratory evaluations

Grading of laboratory values will be assigned programmatically as per the CTCAE version 4.03. The calculation of CTCAE grades will be based on the observed laboratory values only, clinical assessments will not be taken into account.

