2. **on-treatment period:** from date of first dose of eltrombopag to 30 days after the date of the last non-zero dose of eltrombopag (including start and stop date) for patients who completed or discontinued the study early. For ongoing patients, the on-treatment period will be until the cut-off date, as a patient can restart treatment at any time during study.
3. **post-treatment period:** starting at day 30+1 after last non-zero dose of eltrombopag for patients who completed or discontinued the study early. For ongoing patients, there is no post-treatment period.

Safety summaries (tables, figures) include all data considering the on-treatment period definition with the exception of baseline data which will also be summarized where appropriate (e.g. change from baseline summaries). In addition, a separate summary for death including on treatment and post treatment deaths will be provided. In particular, summary tables for adverse events (AEs) will summarize only on-treatment events, with a start date during the on-treatment period (**treatment-emergent** AEs).

However, all safety data (including those from the pre and post-treatment period) will be listed and those collected during the post-treatment period will be flagged.

Additionally, a subgroup analyses on key safety outputs will be provided considering the first 12 months on study. Hence the 12 month on-treatment period is defined as the last non-zero dose + 30 days within the first 12 months on study.

End of Treatment and End of Study

For End of treatment (EOT) derivation, see [Section 2.7.3](#).

Definition of Months and Years

A month will be calculated as $(365.25 / 12) = 30.4375$ days. If duration is to be reported in months, duration in days will be divided by 30.4375. If duration is to be reported in years, duration in days will be divided by 365.25.

For reporting purposes, Month 3 is corresponding to scheduled visit at Week 13 Day1, Month 6 to Week 27 Day 1 visit, Month 9 to Week 39 Day 1, Month 12 to Week 53 Day 1 visit.

Time windows

Time windows for assessments are based on protocol specified windows.

There is a ± 1 day visit window permitted on assessments to take into account scheduling over public holidays, from Week 1 Day 1 to Week 9 Day 1. Also a visit window of ± 3 days is allowed from Week 11 Day 1 to end of treatment.

A visit window of ± 7 days is allowed during the follow-up period for patients with sustained response off treatment.

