2.8.1 Adverse events (AEs)

Coding of AEs

Adverse events will be coded using the latest version of MedDRA at the time of the analysis.

Grading of AEs

AEs will be assessed according to the Common Terminology Criteria for Adverse Events (CTCAE) version 4.03.

The CTCAE represents a comprehensive grading system for reporting the acute and late effects of cancer treatments. CTCAE grading is by definition a 5-point scale generally corresponding to mild (as reported in AE CRF in severity grade variable), moderate (as reported in AE CRF

in severity grade variable), severe (as reported in AE CRF in severity grade variable or “Hospitalization (initial or prolonged)” or “Disability or permanent damage” or “Congenital Anomaly or birth defect” or “Other serious (important medical events)”), life threatening, and death. This grading system inherently places a value on the importance of an event, although there is not necessarily proportionality among grades (a grade 2 is not necessarily twice as bad as a grade 1).

AE summaries

AE summaries will include all AEs occurring during on-treatment period. All AEs collected in the AE (e)CRF page will be listed along with the information collected on those AEs, e.g. AE relationship to study drug, AE outcome etc. AEs starting during the post-treatment period will be flagged in the listings. All information obtained on adverse events will be displayed by patient. Summary tables for adverse events (AEs) will include only AEs that started or worsened during the on-treatment period, the **treatment-emergent** AEs (TEAEs).

TEAEs will be summarized by number and percentage of patients having at least one AE, having at least one AE in each primary system organ class (SOC) and for each preferred term (PT) using MedDRA coding. A patient with multiple occurrences of an AE will be counted only once in the respective AE category. A patient with multiple CTCAE grades for the same preferred term will be summarized under the maximum CTCAE grade recorded for the event. AE with missing CTCAE grade will be included in the ‘All grades’ column of the summary tables.

The incidence of TEAEs will be summarized by system organ class (SOC) and or preferred term, severity based on the CTCAE grades, type of adverse event and relation to eltrombopag.

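### SAP 2.1.1 and SAP 2.8.1 define treatment-emergent AEs differently, and only 2.8.1 keeps the protocol's rule for events that worsen on treatment

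*Protocol*

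**What the plan says.** Three rules appear for the same AE summary tables.

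- **Protocol 12.5.2:** "Summary tables for adverse events (AEs) will include only AEs that started or worsened during the on-treatment period". These are the events it calls treatment-emergent.
- **SAP 2.1.1 (on-treatment assessments and observation periods):** "summary tables for adverse events (AEs) will summarize only on-treatment events, with a start date during the on-treatment period". These too are labelled treatment-emergent, but worsening is not mentioned.
- **SAP 2.8.1:** the tables "will include only AEs that started or worsened during the on-treatment period", which is the protocol rule. Earlier in the same subsection there is a third wording: "AE summaries will include all AEs occurring during on-treatment period".

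SAP section 4, which lists changes to protocol-specified analyses, mentions for 2.1.1 a clarified exposure formula, a definition of planned dose and clarified observation periods. It declares no change to the TEAE definition.

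On collection, Protocol 10.1.1 counts as an AE any untoward occurrence "after providing written informed consent for participation in the study". It sends earlier problems elsewhere: "Conditions that were already present at the time of informed consent should be recorded in medical history of the patient". Screening may run for up to 28 days before treatment starts (Protocol 8.1). Once detected, an AE is reassessed at each "visit (or more frequently, if necessary) of any changes in severity".

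**The concern.** A TEAE flag should have one definition, because every AE table is built on it. Here a programmer who turns to the general definitions would use a start-date test, and one who turns to the AE section would use a started-or-worsened test. Section 2.1.1 cannot be passed over as background: it is also where the SAP defines the 12-month on-treatment period that the month-12 AE, SAE, discontinuation and AESI summaries in 2.8.1 and 2.8.1.1 rely on.

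The two tests disagree on one kind of event: an AE that begins after consent and before first dose, then worsens on eltrombopag. If such an event is dated by its original onset, the start-date test leaves it out of the summaries. Safety and tolerability is secondary objective 10, and the study has a single arm, so the AE percentages are read on their own with no comparator subject to the same rule.

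**Working it through.** The plan gives no figure to reproduce, so the check is a comparison of the rules, case by case.

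| AE history | SAP 2.1.1 (start date) | Protocol 12.5.2 and SAP 2.8.1 (started or worsened) | SAP 2.8.1 third wording (occurring), read literally |
|---|---|---|---|
| A. Starts on treatment | In | In | In |
| B. Starts between consent and first dose, worsens on treatment, one record with original onset date | **Out** | **In** | In |
| C. As B, but the worsening is entered as a new record with its own date | In | In | In |
| D. Starts between consent and first dose, continues unchanged | Out | Out | Arguably in |
| E. Present at consent | Medical history, not an AE | Medical history, not an AE | Medical history, not an AE |

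Three things follow.

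1. **Direction.** Every event counted by the start-date rule is also counted by the started-or-worsened rule, but not the reverse. Following 2.1.1 can therefore leave counts unchanged or lower them, never raise them. The third wording, read literally, is the widest of the three.
2. **Conditions for a loss.** Only row B separates 2.1.1 from the protocol. It needs both that programming follows 2.1.1 and that a worsening stays on the original record. Protocol 10.1.1 requires severity changes to be assessed, but it does not say whether a worsening opens a new dated record, and the SAP does not say so either.
3. **Programmability.** If a single record carries one onset date and only the highest grade, even the started-or-worsened rule cannot be derived, because nothing dates the worsening. The recording convention therefore has to be stated whichever rule is kept.

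**Size.** The documents give no count of AEs with onset between consent and first dose, and none of those that later worsened. The only usable arithmetic is the weight of one patient. SAP section 1 gives 105 enrolled patients; assuming all were dosed and so belong to the Safety Set, 1/105 = 0.0095, or about 0.95 percentage points on the row affected. The number of such patients is unknown, and zero is possible.

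**The case against.** The strongest reply is that this is loose wording, not a competing rule. SAP 2.8.1 is the section that specifies the AE tables, and it carries the protocol rule. The 2.1.1 sentence closes a paragraph on observation periods, and the silence of section 4 fits careless drafting at least as well as an unannounced change. SAP 2.8.1 also provides for several CTCAE grades under one preferred term, and its EudraCT occurrence rule requires a gap of more than one day between records of the same term. Both are compatible with grade changes being entered as separate records, in which case 2.1.1 and 2.8.1 give the same counts. All AEs are listed in any event, and pre-treatment ones are flagged.

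Most of this stands, and it limits the point. It does not remove it: the SAP gives no order of precedence, and the recording convention can only be inferred.

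A reader might also infer more than the documents support:

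- **That the SAP overrides the protocol and drops worsened AEs.** SAP 2.8.1 repeats the protocol rule, so a loss is possible, not established.
- **That many bleeding or steroid-related events will be affected.** Patients enter with platelets below 30 x 10^9/L after recent steroids, but problems already present at consent go to medical history. Only onset between consent and first dose is exposed, and the documents do not say how common that is.
- **That every TEAE table loses the event, or that fewer patients will be reported with any TEAE.** A non-serious worsening that does not lead to discontinuation belongs in neither the SAE nor the discontinuation table under any rule. A patient with another on-treatment AE still counts as having a TEAE. Protocol 10.1.2 treats worsening of a pre-existing condition as a possible SAE in its own right, and SAP 2.3.1 summarises discontinuation reasons from other CRF pages.

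**Conclusion.** The point holds as an internal contradiction in the SAP. Section 2.1.1 defines TEAEs by start date alone; section 2.8.1 and Protocol 12.5.2 include worsening; section 4 declares no change; and no text says which governs. If 2.1.1 is followed, the tables depart from the protocol without a declared change.

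The consequence is conditional. An AE with onset between consent and first dose that worsened on eltrombopag may be missing from the TEAE, AESI and month-12 summaries if programming follows 2.1.1 and the worsening keeps its original onset date. It would still be in the listings. The effect falls on individual preferred-term and grade rows of descriptive tables, and neither the primary endpoint nor any test is touched. The documents do not support the conclusion that on-treatment toxicity is in fact understated.

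**What to change.** - In SAP 2.1.1, replace the start-date condition with the started-or-worsened condition already in SAP 2.8.1 and Protocol 12.5.2, adding no further criterion. Both sources speak only of worsening, so extending the definition to a named grade or seriousness criterion would be a new rule.
- In SAP 2.8.1, bring the sentence about all AEs occurring on treatment under the same rule.
- State how a worsening is recorded and dated: a new record, or the original record with a dated severity change.
- Derive one TEAE flag and apply it to all AE summaries, including the AESI, SAE and month-12 tables.
- Confirm which rule the primary CSR used. SAP section 1 says that report was already final at this version. If it used the start-date rule, say so in the final CSR and report any differences.

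The cost is a few sentences of SAP text, one derivation and a check of the primary outputs. Reported TEAE counts may rise slightly, or not at all.

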12.7 Interim analyses

Not applicable

12.8 Sample size calculation

12.8.1 Primary endpoint

Based on medical experts' advice, it is postulated that approximately 15% of patients who do not respond or relapse after a first round of steroid therapy would have sustained remission by

12 months if on steroid recycling. In this study, at least a 10% higher sustained remission rate is expected by month 12, i.e., a sustained remission rate of at least 25% by 12 months is expected in patients who will receive eltrombopag after failing first-line steroids.

The sample size calculation is based on an exact binomial test for single proportion using a target alpha level of 0.05 and power of 80% to compare the null hypothesis $H_0: P=0.15$ against the alternative hypothesis $H_1: P>0.15$, where P is proportion of patients with sustained remission by Month 12.

A sample size of 101 gives at least 80% power if the true sustained remission rate with eltrombopag is 25% or more with an actual significance level of 0.043. The null hypothesis will be rejected if the number of patients with sustained remission is 22 or more.

Table 12-1 shows the sample size, cut-off, actual alpha, beta and power for different sustained remission rates. PASS 11 (version 11.0.10) is used for the sample size calculation.

Table 12-1 Numeric results for testing $H_0: P = P_0$ versus $H_1: P > P_0$ using exact binomial test statistic

Proportion given H_0 (P_0)	Proportion given H_1 (P_1)	Sample size (N)	Cut-off (Reject H_0 if $R \geq$ This)	Actual Alpha	Actual Beta	Actual Power
0.150	0.250	101	22	0.043	0.196	0.804
0.150	0.300	48	12	0.048	0.181	0.819
0.150	0.350	28	8	0.049	0.182	0.818
0.150	0.400	22	7	0.037	0.158	0.842
0.200	0.300	116	31	0.049	0.193	0.807
0.200	0.350	56	17	0.043	0.194	0.806
0.200	0.400	35	12	0.034	0.195	0.805

At the end of the study, for decision-making purposes, the cut-off will be determined based on the final sample size and the target alpha and beta.

13 Ethical considerations and administrative procedures

13.1 Regulatory and ethical compliance

This clinical study was designed and shall be implemented, executed and reported in accordance with the ICH Harmonized Tripartite Guidelines for Good Clinical Practice, with applicable local regulations (including European Directive 2001/20/EC, US CFR 21), and with the ethical principles laid down in the Declaration of Helsinki.

13.2 Responsibilities of the investigator and IRB/IEC

Before initiating a trial, the investigator/institution must obtain approval/favorable opinion from the IRB/IEC for the trial protocol, written informed consent form, consent form updates, patient recruitment procedures (e.g., advertisements) and any other written information to be provided to patients. Prior to study start, the investigator is required to sign a protocol signature page confirming his/her agreement to conduct the study in accordance with these documents and all of the instructions and procedures found in this protocol and to give access to all relevant data

and records to Novartis monitors, auditors, Novartis Quality Assurance representatives, designated agents of Novartis, IRBs/IECs, and regulatory authorities as required. If an inspection of the clinical site is requested by a regulatory authority, the investigator must inform Novartis immediately that this request has been made.

13.3 Publication of study protocol and results

The protocol will be registered in a publicly accessible database such as clinicaltrials.gov and as required in EudraCT. In addition, after study completion (e.g., defined as last patient last visit) and finalization of the study report the results of this trial will be submitted for publication and posted in a publicly accessible database of clinical trial results, such as the Novartis clinical trial results website and all required Health Authority websites (e.g. Clinicaltrials.gov, EudraCT etc.).

For details on the Novartis publication policy including authorship criteria, please refer to the Novartis publication policy training materials that were provided to you at the trial investigator meetings.

13.4 Quality Control and Quality Assurance

Novartis maintains a robust Quality Management System (QMS) that includes all activities involved in quality assurance and quality control, to ensure compliance with written Standard Operating Procedures as well as applicable global/local GCP regulations and ICH Guidelines.

[figure not shown]
Audits of investigator sites, vendors, and Novartis systems are performed by auditors, independent from those involved in conducting, monitoring or performing quality control of the clinical trial. The clinical audit process uses a knowledge/risk based approach.

Audits are conducted to assess GCP compliance with global and local regulatory requirements, protocols and internal SOPs, and are performed according to written Novartis processes.

14 Protocol adherence

This protocol defines the study objectives, the study procedures and the data to be collected on study participants. Additional assessments required to ensure safety of patients should be administered as deemed necessary on a case by case basis. Under no circumstances including incidental collection is an investigator allowed to collect additional data or conduct any additional procedures for any purpose involving any investigational drugs under the protocol, other than the purpose of the study. If despite this interdiction prohibition, data, information, observation would be incidentally collected, the investigator shall immediately disclose it to Novartis and not use it for any purpose other than the study, except for the appropriate monitoring on study participants.

Investigators ascertain they will apply due diligence to avoid protocol deviations. If an investigator feels a protocol deviation would improve the conduct of the study this must be considered a protocol amendment, and unless such an amendment is agreed upon by Novartis and approved by the IRB/IEC and health authorities, where required, it cannot be implemented.

